Over the years, an increased understanding of how a child's physiology interacts with a ventilation system has led to improved technologies. Whereas traditional ventilation modalities such as endotracheal intubation is invasive and can lead to tracheal damage with prolonged use (3), non-invasive ventilation (NIV) modalities avoid the risks associated with tracheal intubation. In addition, NIV can be used at an earlier stage compared to tracheal intubation, and facilitates gradual weaning when used intermittently (4). Two modalities that are widely used in intensive care units are continuous positive air pressure (CPAP) and bilevel positive air pressure (BiPAP). Both of these modalities operate using positive airway pressure to keep the trachea open. CPAP machines are set to deliver a continuous stream of air, while BiPAP machines offer a different level of pressure for inhalation versus exhalation. Collectively, use of these modalities and their benefits are well-documented, including improved gas exchange, decreased respiratory and heart rate, and decreased inspiratory work of breathing (5-8). Building on these strengths, neurally adjusted ventilator assist (NAVA) is emerging as an alternative form of the bi-level NIV with application in multiple settings.

With NAVA support, delivery of positive pressure is based on the electrical activity of the diaphragm (Edi) via a nasogastric (NG) catheter that is placed on the phrenic nerve, which runs along the esophagus. This concordance between the Edi and NAVA lends itself to synchrony between the patient and ventilator, as well as respiratory support that is proportional to the neural effort of the patient (9). Synchronous ventilation support results in decreased neural drive and

improved comfort in intubated patients (10, 11). Prior research has examined the use of NAVA in different patient settings, most notably the PICU and NICU as summarized in **Table 1**. These studies suggest NAVA may contribute to decreased sedation needs (12), improved synchrony (10, 13, 14), improved breath-to-breath mechanical variability (10), increased patient comfort (10), and reduction of wasted breathing efforts (13). In these populations, evidence supports the safety and feasibility of NAVA (12, 15).

Reference	Setting	Design	Intervention	Results
Kallio et	PICU	Randomized	Conventional ventilation (CV)	Ventilation duration: 3.3hrs NAVA and 6.6hrs
al 2014		controlled trial	or NAVA	CV (P=0.17); Sedation amount: 0.80units/hr

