This will be a prospective randomized study comparing outcomes of pediatric patients who are treated with NAVA versus BiPAP respiratory support following cardiac surgery. Subjects will include pediatric CVCC patients who undergo cardiac surgery from October 2016 through October 2017 and who are up to 12 months of age. As patients recover from cardiac surgery, they are extubated and may require further respiratory support. If so, they receive CPAP support and then are transitioned to one of two modalities: either NAVA or BiPAP support. Both modalities are routinely used in the Children's CVCC, and the investigators will compare if one modality produces more favorable outcomes than the other. Following CPAP, enrolled subjects will be randomized to receive either NAVA or BiPAP, and their remaining clinical course will follow standard care. Specific measures following initiation of respiratory support will be collected, in addition to characteristics of the operative procedure and patient diagnoses. The study aims to compare duration of respiratory support, sedation requirements, and hospital length of stay between the two modalities.

Time Frame/Duration

This study will be conducted over an 18-month period to allow for subject enrollment, data collection, analysis, and manuscript preparation.

Activity		Month																
	1	2	3	4	5	6	7	8	9	10	11	12	13	14	15	16	17	18
IRB approval																		
Recruitment/enrollment																		
Data collection/ chart abstraction																		
Analysis																		

Manuscript preparation									

Analysis

Sample Size

We will enroll all consecutive patients who are eligible for inclusion in the 12-month enrollment period and consent to participation, up to 40 patients. An interim analysis will be performed after 20 patients are enrolled to assess means and variance of the primary outcomes, and reassess sample size.

Analytic Approach

Exploratory analysis methods will be used to describe the enrolled patient population, including mean and standard deviation for continuous variables such as length of hospital stay, sedation needs, and intubation as well as frequency and percentage for categorical variables such as STAT score and type of non-invasive PPV.

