For the continuous outcomes of interest (duration of non-invasive respiratory support, length of hospital stay and sedation needs), either a two-sample t-test or non-parametric Mann-Whitney U test will be used to compare those patients who received NAVA or BiPAP. For categorical variables, either a chi-square test or Fischer's exact test will be used to compare the two groups. Additional regression analysis will adjust for procedure severity.

Statistical significance will be defined as p < 0.05.

5. Subjects

Subjects

We plan to enroll 40 subjects 0 to 12 months of age at time of cardiac surgery over a 1 year period.

Identification of Subjects, Recruitment, and Enrollment

Potential subjects will be identified by monitoring the cardiovascular surgery schedule, and eligibility will be confirmed by the provider. Patients who meet all of the inclusion criteria and none of the exclusion criteria will be approached for consent by study staff. Not all cardiac patients receive NIV support postoperatively, and the decision to provide NIV support is not made by the provider until after the surgery. This will happen either while the patient is intubated, or immediately following extubation. Written informed consent will be sought from parents/guardians. Assent will not be sought in this young patient population. Patients who enroll will be assigned a unique study ID. A log of enrolled subjects will be maintained, and will only be accessible by approved study staff. The target enrollment is 40 patients.

Inclusion Criteria:

- Postoperative cardiac surgery patients admitted to the CVCC
- Recommended for NIV respiratory support following extubation, per provider discretion
- 0-12 months of age

Exclusion Criteria:

- Tracheostomy in place at time of cardiac surgery
- Chronic lung disease
- Pre-operative non-invasive respiratory support

6. Study Procedures

Data Requirements

The data elements will be collected by the research study staff from the subject's electronic medical record. These will include:

- Demographic Data (name, date of birth, age at admission, admission date/time, cardiac diagnosis, comorbidities)
- Operative Data (surgeon, date of procedure, intubation/extubation date/time, date/time returned to CVCC)
- Adverse Event Information (description of event and day post-cardiac surgery that the event(s) took place)

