- Medication Data (daily amounts of dexmedetomidine, fentanyl (total fentanyl and boluses of pca fentanyl), midazolam, morphine, lorazepam for up to 14 days postoperatively, date/time patient is on/off the above medications)
- Post-Operative Respiratory Support Data (type of non-invasive respiratory support used, date/time on off CPAP, date/time on/off biPAP/NAVA)
- Pain and Sedation Score Data (daily FLACC/SBS scores for up to 14 days postoperatively)
- Discharge Data (discharge date/time, length of hospital stay, survival at discharge, date/time of death [if applicable], cause of death [if applicable])

Visit Schedule

Eligible patients will be recruited during their admission to the CVCC. Upon enrollment, patients will be randomized to receive either NAVA or BiPAP. What respiratory modality the patient will receive will be determined by drawing a slip of paper from a sealed envelope. Following randomization and provision of respiratory support, patient care will be per standard care. Patient data will be only collected for the reference admission period. There will be no follow-up visits or activities required of the patient for this study following enrollment.

Drug/Device, Handling, Storage (If Applicable)

All devices in this study are currently used and stored in the CVCC. They will continue to be used as per CVCC SOPs.

7. Risks/Benefits

Potential Risks

Subjects will be randomized to respiratory support treatments that are already incorporated into standard care. The potential risks from these treatments are no more than those experienced as part of standard care. There is a risk associated with privacy of personal health information, and there is a risk of breach of confidentiality.

Methods to Minimize Risks

Both NAVA and BiPAP are non-invasive modalities that are safely used in standard care. Providers will follow SOPs for the use of NAVA and BiPAP support to minimize risks. If complications occur, standard care will be provided and patients will be treated accordingly. Electronic data will be stored on secure password-protected computers in limited access files, in a locked office suite. Any paper records will be stored in locked cabinets that only approved study staff have access to. This is a single-site study, and no identifiable patient data will be shared outside of the IRB-approved study staff. Any results from the study will be published in aggregate form, preventing any individual patient's data from being identified.

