Potential Benefits

The subjects will not gain added benefit directly from this study, since the treatments provided will be consistent with standard care. This study will contribute to understanding how outcomes may vary with different modalities of respiratory support in this patient population.

Adverse Events

The research staff will document any adverse events that occur in the admission period for enrolled patients following provision of NAVA or BiPAP. Enrolled patients will be monitored in the CVCC, and standard care will be provided. Any unanticipated problems involving risks to the subjects or other (UPIRTSOs) will be reported to the IRB within 10 days.

Stopping Rules and Data Safety Monitoring Plan

The research interventions are both consistent with the standard of care for the study population. No stopping rules are planned.

8. Administrative Procedures

Patient Confidentiality

All study data will be stored on a secure password-protected computer in the locked research office. Patient study files will be stored in a locked cabinet within the research office. Subjects will be given a unique study ID number when entered into the RedCap study database.

Data Management

Data will be collected on paper documents and will be securely stored in a locked cabined within the research office. Only the research study team will have access to these paper documents. Once the data has been collected on the source documents, the data will be entered into a study-specific RedCap database, which is a secure network that is password-protected. All of the study data will be securely stored for up to 3 years or completion of the study and all subsequent publications and presentations of the study results.

9. References

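### The plan gives two randomisation times, and under the earlier one the arm could be known before it is settled that bi-level support will start

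*Combined protocol and SAP*

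**What the plan says.** Two statements set the time of randomisation.

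- Section 4, Study Design: "Following CPAP, enrolled subjects will be randomized to receive either NAVA or BiPAP". The subjects are already enrolled, and CPAP comes before the draw.
- Section 6, Visit Schedule: "Upon enrollment, patients will be randomized to receive either NAVA or BiPAP". The draw is made at enrolment, by taking a slip from a sealed envelope.

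Three other places decide whether the difference matters.

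- Section 5, Inclusion Criteria, requires only that the infant be "Recommended for NIV respiratory support following extubation, per provider discretion". Bi-level support is not specified.
- Section 5, on identification and recruitment, says that "the decision to provide NIV support is not made by the provider until after the surgery", and then: "This will happen either while the patient is intubated, or immediately following extubation".
- The background, in its account of non-invasive ventilation, says: "Two modalities that are widely used in intensive care units are continuous positive air pressure (CPAP) and bilevel positive air pressure (BiPAP)". CPAP is thus one form of NIV.

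The Analytic Approach in Section 4 compares infants by the modality they received. It names no analysis set and has no rule for a randomised infant who receives neither. Section 7, Adverse Events, records events "following provision of NAVA or BiPAP".

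**The concern.** The time of randomisation fixes who is in the trial and what staff know when they make later decisions. No blinding is described. If the slip is drawn while an infant is intubated or newly extubated, the move from CPAP to a bi-level device is decided with the arm known. An infant who never makes that move has been randomised but has neither device to be classified under, so the planned comparison leaves that infant out. If such losses differ between arms, the groups compared are no longer those formed by randomisation. Even if losses are balanced, a trial of at most 40 infants becomes smaller. The timing also decides whether CPAP time falls before or after randomisation, which bears on Aim 1, the duration of non-invasive support.

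**Working it through.** **Do the two rules differ?** Section 4 treats enrolment and randomisation as separate events with CPAP before the second. Section 6 makes them one event. They coincide only if enrolment is completed at the end of CPAP. Section 5 allows the eligibility condition to be met earlier, while the infant is intubated or just after extubation. No visible passage says that enrolment waits. The Study Schema in Appendix 3 is listed but its content is not shown.

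**Is there a figure to reproduce?** No. The target of 40 is a cap on a 12-month enrolment period. The plan states no power, effect, SD or allocation ratio.

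**Inputs for an illustration.** From the plan: 40 infants in total, a significance level of 0.05, and the Mann-Whitney test as one of its two options. Assumed: 1:1 allocation (20 per arm), a two-sided test, log-normal duration with log-SD 0.8, a true halving of duration (ln 2 / 0.8 = 0.693 / 0.8 = 0.87 SD on the log scale), and a share f of 10, 20 or 30% who never receive bi-level support.

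**Simulation.** Log durations are drawn as Normal(0, 0.8) for BiPAP and Normal(ln 0.5, 0.8) for NAVA. Power is the share of simulated trials with p < 0.05. Repeat runs agree to within about two percentage points.

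- *Non-recipients removed*, as the planned comparison implies: the number left is 40 × (1 − f), with equal loss per arm.
- *Non-recipients kept*: 20 × f = 2, 4 or 6 infants in the NAVA arm simply show no effect, and the BiPAP arm is unchanged.

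| f | Infants left if removed | Power if removed | Power if kept |
|---|---|---|---|
| 0% | 40 | 74% | 74% |
| 10% | 36 | about 67% | about 62% |
| 20% | 32 | about 62% | about 53% |
| 30% | 28 | about 56% | about 42% |

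**Cross-check with a normal approximation and equal f in both arms.** Take as reference the difference detectable with 80% power at 20 per arm: (1.960 + 0.842) × √(2/20) = 0.886 SD.

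- Removed: power = Φ(2.802 × √(1 − f) − 1.960). For f = 10/20/30% this is Φ(0.698), Φ(0.546), Φ(0.384) = 76/71/65%.
- Kept: power = Φ(2.802 × (1 − f) − 1.960). For f = 10/20/30% this is Φ(0.562), Φ(0.282), Φ(0.001) = 71/61/50%.

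The starting level differs but the pattern is the same. Neither calculation includes the bias that would follow if removal differed by arm.

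**The case against.** The strongest reply is that the plan describes no infant who stops at CPAP. Section 4 has every infant who needs further support receive CPAP and then move to NAVA or BiPAP. Read literally, f is zero and none of the losses above occurs. The paragraph before the Research Question also speaks of NIV in the bi-level sense. A reader might infer from the inclusion wording that the trial will randomise infants who need only CPAP. The documents allow that but do not show it, and they give no rate.

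A reader might also say that the two rules can never both be followed. That goes too far. Section 6 goes on to mention randomisation and provision of support together, and the window in Section 5 may refer to the provider's decision and not to enrolment. If enrolment closed at the end of CPAP, both rules would hold. Section 4 tells against this, because it speaks of enrolled subjects being randomised later.

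On safety, a reader might infer that infants who receive neither device vanish from the data. This is only partly so. Data Requirements in Section 6 collects adverse events by day after surgery with no device condition, and survival and death are recorded. The conflict is between that list and the narrower wording in Section 7.

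Lastly, the power figures rest on assumed inputs, and the kept scenario is a simple model that leaves the BiPAP arm untouched. Dilution is also not what the plan's wording implies, since a comparison by modality received excludes these infants. That clinicians would drop infants because they know the arm is nowhere stated.

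What stands is the unreconciled timing, an inclusion criterion wider than the comparison, and no rule for a randomised infant who receives neither device.

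**Conclusion.** The concern holds as a conflict in the text with a conditional consequence. Sections 4 and 6 give different randomisation times. Under the Section 6 rule, allocation can precede the point at which bi-level support is settled. If some infants then receive neither device, the written comparison removes them after allocation. The cost is about 67/62/56% power at 10/20/30% non-receipt, against 74% with none, plus possible bias if removal differs by arm. Keeping them would give about 62/53/42% under the simple no-effect model. These figures assume 20 per arm, a log-SD of 0.8, a halved duration and the stated shares, none of which beyond the total of 40 comes from the plan. The true share could be near zero. Confidence is high for the conflict and moderate for the consequence.

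**What to change.** Reconcile Section 4 (Study Design) and Section 6 (Visit Schedule) to one randomisation point, and make the Study Schema agree.

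1. Take consent early, but open the envelope only once the provider has decided to start bi-level support. That decision stays with the provider and is made before the arm is known.
2. Word the inclusion criterion as a recommendation for bi-level NIV support (NAVA or BiPAP).
3. State that every randomised infant is analysed in the assigned arm, in place of the comparison by modality received. With randomisation at the decision to start, few infants should receive neither device, so this should cost little power.
4. Count outcomes and adverse events from randomisation, replacing the Section 7 wording that starts at provision of the device.

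The cost is protocol wording. The one small downside is that some consented infants will never be randomised and must be logged as screened.

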NAVA has recently been adopted for non-invasive respiratory support in the Children's Hospitals and Clinics of Minnesota CVICU, the cardiovascular care center (CVCC). Close to 10% of CVCC post-operative patients receive a form of bi-level NIV support, either NAVA or BiPAP. The frequency of NIV use in neonates (0 to 28 days of age) can be 30% or higher. We propose a randomized study to compare clinical outcomes following use of NAVA versus BiPAP in CVCC patients following cardiac surgery. Specifically, we will compare duration of NIV, duration of sedation, and hospital length of stay.

Research Question

Is the use of synchronized biphasic support with NAVA associated with shorter duration of noninvasive respiratory support, less sedation requirements, and reduced hospital length of stay compared to conventional BiPAP?

4. Study Design and Methodology

Aim 1: To assess whether the use of neurally adjusted ventilator assist (NAVA) is associated with a shorter duration of non-invasive respiratory support compared to conventional BiPAP. **Aim 2:** To assess whether the use of neurally adjusted ventilator assist (NAVA) is associated with less sedation requirements compared to conventional BiPAP.

Aim 3: To assess whether the use of neurally adjusted ventilatory assist is associated with reduced hospital length of stay compared to conventional BiPAP.

Hypothesis: Synchronized biphasic support with NAVA will be associated with shorter duration of non-invasive respiratory support, less sedation requirements, and reduced hospital length of stay.

Overview/Scope

Study Design

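### Allocation is described only as a paper draw from a sealed envelope; with no sequence, blocks, strata or draw record stated, it cannot be audited as written

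*Combined protocol and SAP*

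**What the plan says.** Section 6, Visit Schedule, states "Upon enrollment, patients will be randomized to receive either NAVA or BiPAP" and then gives the mechanism: "What respiratory modality the patient will receive will be determined by drawing a slip of paper from a sealed envelope". Nothing else in the available text describes how the allocation is produced or protected. The Study Design text in Section 4 places randomisation after CPAP, which is not obviously the same moment as enrolment.

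The surrounding design matters for reading that sentence:

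- **Size.** The Sample Size paragraph of Section 4 reads: "We will enroll all consecutive patients who are eligible for inclusion in the 12-month enrollment period and consent to participation, up to 40 patients". The same section adds: "An interim analysis will be performed after 20 patients are enrolled to assess means and variance of the primary outcomes, and reassess sample size".
- **Age mix.** Section 5, Subjects: "We plan to enroll 40 subjects 0 to 12 months of age at time of cardiac surgery over a 1 year period". No age strata are named.
- **Neonates.** The background, just before the Research Question, says "Close to 10% of CVCC post-operative patients receive a form of bi-level NIV support, either NAVA or BiPAP" and "The frequency of NIV use in neonates (0 to 28 days of age) can be 30% or higher".
- **Adjustment.** Section 4, Analytic Approach: "Additional regression analysis will adjust for procedure severity". Age is not named as a covariate.
- **Entry.** Section 5 makes the recommendation for non-invasive support a matter of provider discretion, and the provider also confirms eligibility.
- **Care after allocation.** Standard care, with no blinding described.

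**The concern.** Randomisation protects a trial in two ways, and the plan documents neither fully.

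The first is concealment. Whoever enters a patient must not know or be able to influence the next assignment. Here entry turns on clinical judgement, the two modalities can be told apart in use (NAVA needs its own catheter), and two of the three outcomes, duration of support and sedation, are partly set by the people giving care. If a slip were drawn again, or an infant held back, nothing described in the plan would prevent it or show it afterwards. Selection bias of that kind cannot be reliably repaired in the analysis.

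The second is balance. With at most 40 infants from birth to 12 months, no blocks and no strata, arm sizes and age mix may drift apart by chance. The only adjustment planned is for procedure severity.

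**Working it through.** The plan gives no effect size, standard deviation or power, so its figure of 40 cannot be reproduced. The checks below take 40 as given.

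**Inputs.** N = 40 (Section 4, Sample Size, and Section 5). Ratio 1:1 is assumed, because none is stated. The neonate share of enrolled infants is not given; 25% to 75% is assumed. The test is taken as two-sided at 0.05, because the plan gives the level but not the sidedness.

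**1. Arm sizes, independent 1:1 draws.** With X ~ Binomial(n, 0.5), the chance of a split of k:(n−k) or worse is 2 × P(X ≥ k).

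| n | Split or worse | Chance |
|---|---|---|
| 40 | 24:16 | 26.8% |
| 40 | 25:15 | 15.4% |
| 40 | 26:14 | 8.1% |
| 20 (interim) | 13:7 | 26.3% |
| 20 (interim) | 14:6 | 11.5% |

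**2. Arm sizes, if one pool of 20 + 20 slips is drawn without replacement.** The arms are exactly 20:20 at 40 patients. By the hypergeometric distribution, a split of 13:7 or worse at the 20-patient look has an 11.3% chance. If only 30 infants enrol, 17:13 or worse has a 27.3% chance.

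**3. Cost of unequal arms.** The variance of a difference in means, relative to 20:20, is (1/n₁ + 1/n₂)/(1/20 + 1/20). At 25:15 this is 0.1067/0.1 = 1.067; at 26:14 it is 0.1099/0.1 = 1.099. For power, take the standardised effect d = 0.886 that gives 80% at 20:20 (an assumption) and use Φ(d√[n₁n₂/(n₁+n₂)] − 1.96):

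- 25:15: √(375/40) = 3.062, so Φ(2.713 − 1.96) = 77.4%.
- 26:14: √(364/40) = 3.017, so Φ(2.673 − 1.96) = 76.2%.

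The loss is 2.6 points at 25:15 and 3.8 points at 26:14.

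**4. Neonate share.** Let m of the 40 be neonates. Under simple allocation, the neonates and the older infants assigned to an arm are independent Binomial(m, 0.5) and Binomial(40−m, 0.5), enumerated exactly. With arms fixed at 20:20, the number of neonates in one arm is hypergeometric.

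| Neonates among 40 | Simple: gap ≥ 20 points | Simple: gap ≥ 30 | Fixed 20:20: gap ≥ 20 | Fixed 20:20: gap ≥ 30 |
|---|---|---|---|---|
| 10 or 30 (25% or 75%) | 17.4% | 3.5% | 27.3% | 6.5% |
| 16 or 24 (40% or 60%) | 22.6% | 6.3% | 33.3% | 10.5% |
| 20 (50%) | 26.8% | 8.1% | 34.3% | 11.3% |

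With fixed arms and an even m, the gap moves in steps of 10 points, so the 20-point column includes gaps of exactly 20.

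**5. After the fix.** With blocks of 4 in two age strata, each stratum can end at most 2 out of balance. The worst total is therefore a difference of 4, which is 22:18, with power Φ(0.886 × √(396/40) − 1.96) = 79.6%. The worst neonate gap arises when the strata err in opposite directions: (m+2)/40 − (m−2)/40 = 4/40 = 10 points.

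**The case against.** The strongest reply is that this is silence, not a stated fault. The sentence fits individually prepared envelopes opened in order as well as it fits one pooled envelope. The word sealed offers some protection. Section 5 requires a study ID and an enrolment log, and Section 6 collects the type of support with times on and off. Consecutive enrolment is planned. Appendices 3 and 4 are listed, but only their titles were available. All of this stands, and it limits the claim to what is undescribed. It does not answer the point, because the enrolment log and the treatment times show who entered and what each infant received, not what was drawn or how often.

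Three stronger readings are tempting and not supported:

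- **The protocol allows a second draw.** It does not say so. It states nothing that would prevent or record one.
- **Neonate status is an established prognostic factor here.** The background shows that neonates receive non-invasive support more often. Every enrolled infant has already been recommended for it, and nothing in the plan shows that age predicts duration, sedation or stay among them. Age is a plausible factor only, and the bias from an imbalance cannot be quantified.
- **Imbalance is likely.** The chances above run from about one in six to one in three for a 20-point gap, and they depend on an assumed neonate share. The loss of power is minor. A chance imbalance in age can also be adjusted for, since date of birth and age at admission are collected.

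**Conclusion.** The point holds as a cheap and worthwhile improvement, not as a fatal flaw. The main weakness is that the allocation, as described, cannot be audited in a trial with discretionary entry, no described blinding and outcomes that caregivers can influence. That leaves an avoidable risk of selection bias; the documents give no ground for saying that such bias will occur.

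Imbalance is secondary. A 25:15 or worse split has a 15% chance under simple 1:1 allocation, with a power cost under 3 points at 25:15. A neonate gap of 20 points or more has a 17% to 27% chance, or 27% to 34% with arms fixed at 20:20. These figures rest on a 1:1 ratio, a final N of 40 and a neonate share of 25% to 75%, of which the plan states only the 40. That the trial is unblinded is inferred from the absence of any description.

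**What to change.** Replace the draw with the following, and write it into Section 6:

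1. A computer-generated 1:1 list in randomly varying small blocks, preferably stratified by neonate (0 to 28 days) versus older. Make it long enough to cover any increase after the interim reassessment.
2. Concealment in sequentially numbered, opaque, sealed envelopes, or in a module of the RedCap database already planned in Section 8. Either should be prepared by someone who neither enrols nor treats patients.
3. The study ID, date and time written on each envelope before it is opened, with every envelope kept.
4. Neonate status or age, already collected, added to the planned severity-adjusted regression.
5. One statement of when randomisation happens, reconciling the Study Design text with the Visit Schedule.

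If such safeguards already exist in practice, describing them settles the concealment part. The cost is a few hours of preparation, one further regression term, and slight predictability at block ends, which varying the block size limits. Stratifying is a preference; if it is dropped, item 4 matters more.

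### Adverse event documentation starts when NAVA or BiPAP is provided, not at randomisation, so events between assignment and device start fall outside the rule

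*Combined protocol and SAP*

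**What the plan says.** Section 7 (Adverse Events) is the only place that says when adverse event documentation begins: "The research staff will document any adverse events that occur in the admission period for enrolled patients following provision of NAVA or BiPAP".

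The time of assignment is given in two ways. Section 6 (Visit Schedule) says "Upon enrollment, patients will be randomized to receive either NAVA or BiPAP". Section 4 (Study Design) says "Following CPAP, enrolled subjects will be randomized to receive either NAVA or BiPAP". Section 6 then names assignment and device start as two steps, in that order: "Following randomization and provision of respiratory support, patient care will be per standard care".

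The adverse event item in Section 6 (Data Requirements) is "Adverse Event Information (description of event and day post-cardiac surgery that the event(s) took place". It has no start point and is timed by day only. Respiratory support in the same list is timed more finely: "date/time on off CPAP, date/time on/off biPAP/NAVA". The time of randomisation is not on the list, nor is the time of catheter placement.

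The background describes NAVA as a mode in which "delivery of positive pressure is based on the electrical activity of the diaphragm (Edi) via a nasogastric (NG) catheter".

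**The concern.** In a randomised comparison, safety follow-up should start at assignment and cover everyone assigned. Here it starts at a later event, the provision of the device. That has two consequences. Whatever happens while an infant waits for the assigned device is not documented as an adverse event. An infant who is assigned but never starts the device has no adverse events documented under the rule at all. The safety set is then defined by something that happens after randomisation, and the two groups in an adverse event table need not be the groups that were randomised.

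A second worry is that the gap may contain a step belonging to one arm. NAVA depends on a catheter signal, and the documents describe no such catheter for BiPAP. If placement falls between randomisation and provision, the rule could omit procedural events in the NAVA arm that have no counterpart in the other.

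The trial plans no stopping rules and aims for 40 infants, so the adverse event record is most of what it will be able to say about safety.

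**Working it through.** No arithmetic applies. The documents give no adverse event rate, no catheter event rate and no time from randomisation to device start. The check is to set the sections side by side.

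1. **Where the window opens.** Section 7 ties documentation to the time after NAVA or BiPAP has been provided.

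2. **Where assignment happens.** Section 6 puts it at enrolment and Section 4 puts it after CPAP. Either way it precedes provision, because Section 6 lists randomisation and provision as successive steps. A gap therefore exists on both readings.

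3. **How long the gap is.** This depends on which section is followed.
   - On the Section 6 reading, the gap can be long. Section 5 (Identification of Subjects, Recruitment, and Enrollment) says "This will happen either while the patient is intubated, or immediately following extubation", where the first word may refer to the decision on non-invasive support or to the approach for consent. If enrolment and assignment occur then, the gap can include the rest of intubation, extubation and the whole CPAP phase.
   - On the Section 4 reading, the gap is only the time from the end of CPAP to the start of the assigned device.

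4. **What other routes capture.** Section 6 collects survival at discharge and the date, time and cause of death for the admission, regardless of device start. Section 7 requires unanticipated problems to be reported to the IRB within 10 days, also without that limit. Neither route covers a non-fatal event that is not an unanticipated problem.

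5. **Whether Section 6 closes the gap.** Its adverse event item has no start point and counts days from surgery, so it could be read as covering the whole postoperative stay. It is an entry in a list of data elements, whereas Section 7 states which events staff document. The two do not define the same window, and nothing says which governs.

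6. **Whether the window can be applied as written.** Device start has a date and time, while an adverse event has only a postoperative day. An event on the day of device start cannot be placed before or after it, so even the Section 7 rule is ambiguous on that day.

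7. **Whether the omission differs by arm.** That would need catheter placement to fall after randomisation and before provision, to happen in the NAVA arm only, and not to count as part of providing NAVA. The background establishes only that NAVA works through a catheter. None of the three conditions is stated.

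**The case against.** The strongest reply is that little is actually lost. Deaths and unanticipated problems are captured whether or not the device starts, and the Section 6 data item is not limited to the time after device start. An infant who never reaches the device is therefore not without safety data. This stands, and it rules out saying that all events in the gap disappear. What remains is the ordinary non-fatal adverse event, which neither of the first two routes covers and on which Sections 6 and 7 disagree.

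A reader might infer that the rule biases the safety comparison in favour of NAVA, because catheter complications go uncounted in that arm alone. The documents do not support this. They do not say when the catheter is placed, whether BiPAP infants have one, or whether providing NAVA includes placing it. If placement comes before randomisation, or counts as part of provision, the one-arm loss disappears. Events during intubation or CPAP precede both devices, and omitting them does not in itself favour either arm. A figure for the number of placement events missed would come entirely from an assumed rate, so none is given here.

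It can also be said that safety is not an aim of the trial: the three aims are duration of support, sedation and length of stay. Both modalities are described as standard care. That limits what is at stake, but the protocol does commit to documenting adverse events, and randomisation decides which infants receive which modality.

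Finally, the data collection forms in Appendix 4 are not available for review and may record onset times. If they do, the timing point concerns only the protocol text.

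**Conclusion.** The concern holds in a limited form. As written, Section 7 starts adverse event documentation after assignment. It leaves out non-fatal events between randomisation and device start, and those in a randomised infant who never starts the assigned device, except where they qualify as unanticipated problems. Section 6 does not resolve this, because its adverse event item has no start point and conflicts with Section 7.

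The size cannot be estimated from the documents. The gap ranges from a short interval after CPAP to a period that includes part of intubation and all of CPAP, depending on whether Section 4 or Section 6 describes when infants are randomised. A difference between arms is possible if catheter placement falls in the gap, but neither its size nor its direction can be determined.

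The conclusion rests on two readings: that Section 7 governs which events are documented, and that provision means the start of the assigned device. The change is worth making because it is cheap and gives a safety comparison by assigned arm.

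**What to change.** In Section 7 (Adverse Events), replace the current rule with wording to this effect: *adverse events are documented for every randomised infant from the time of randomisation to the end of the admission, whether or not the assigned device is started, including any event during Edi-catheter placement after randomisation, and are tabulated by assigned arm.*

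In Section 6 (Data Requirements), align the adverse event item with that window and record the onset date and time of each event in place of the postoperative day alone. Add the date and time of randomisation. Device on and off times are already collected at this resolution.

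Reconcile Sections 4 and 6 on when randomisation occurs, so that the start of the window is unambiguous.

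The cost is wording in these sections and a few form fields. Staff will abstract a slightly longer stretch of a record they already read. Some events unrelated to either device will be counted in both arms.
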